9.7 Modeling of the Secondary and Tertiary Endpoints

Confidence intervals (95%) and p-values will be based on means at each time point using a one sample t-test; change from baseline summaries will also be provided in this fashion.

In addition, for analyses which involve change from baseline (tertiary endpoints), each TV-eFRM 02880

post-surgical measurement will be represented as a change from baseline, with baseline measurement and other possible factors of interest included as covariates in a linear regression model. These analyses are deemed exploratory, with no adjustment for multiplicity and no labeling claims based on the results. PROC TTEST and PROC REG will be used for the analyses. As noted in 9.8.4, the analysis is repeated in each imputed data set and thereafter aggregated. Aggregated results will be reported.

The Kaplan-Meier methods will be used to report results for survival endpoints. Survivorship point estimates and 95% confidence intervals will be presented for a time point if at least 40 subjects remain at risk. The conventional Greenwood estimate will be used to calculate the variance and the complementary log-log transformation will be used to construct 95% confidence intervals using PROC LIFETEST.

9.8 Missing Data

9.8.1 Primary endpoint

As detailed in the CIP, participants who withdraw prior to the 24-month follow-up visit (i.e., lost to follow-up) and did not experience a continuous RLL around the humeral component, a serious adverse device-related event or a revision surgery in which the humeral component was removed, would have missing data on their clinical outcomes, which will be addressed using imputation. Imputed values will be used to determine whether patients who withdraw prior to the 24-month follow-up visit are categorized as successes or failures on the primary endpoint. Specifically, determining success or failure on the primary endpoint for each patient withdrawing prior to the 24-month follow-up visit will be based on imputed values of clinical outcomes that make up the primary endpoint. Patients will be scored as a failure on the primary endpoint if their imputed values indicate continuous RLL around the humeral prosthesis or a revision in which the humeral component was removed or a SADE took place or the adjusted Constant-Murley score ≤ 85.

9.8.2 Survival Endpoints

Safety, secondary and tertiary endpoints include survival outcomes. Patients with missing data resulting from withdrawal will be treated as censored, with their censoring time based on the date of last assessment.

9.8.3 Continuous Secondary and Tertiary Endpoints

Continuous secondary and tertiary endpoints include the adjusted Constant Murley Score, Oxford Shoulder score and the EQ-5D-5L scores. Missing data that could impact the proposed analysis would result from participants withdrawing from the study as well as missed intermediate assessments. In either case missing data will be handled using imputation.

9.8.4 Method of Imputation

Multiple imputation will be performed using a fully conditional specification [10], given the need to impute values for binary variables. Fifty imputations will be performed. In order to combine results across imputed datasets, the parameter estimate will be calculated using an average of estimates obtained across datasets and the variance calculated using Rubin's method [11]. All calculations will be performed in SAS and imputations will be performed using PROC MI and aggregated using PROC MIANALYZE.

9.8.5 Imputation Model

A single imputation model will be used to impute values for the primary, secondary and tertiary endpoints (not including survival endpoints). The variables used to define the primary endpoint are presence/absence of a: continuous RLL around the humeral component, a serious adverse device-related event, revision surgery of the humeral component and the adjusted Constant-Murley score. For the adjusted Constant-Murley score, we will create separate variables for scores obtained at each assessment to include in the imputation model. For the other variables that make up the primary endpoint, partitioning by time could produce computational problems, therefore we will consider a model in which the presence/absence of the outcomes will be imputed irrespective of their timing. Even with this simplification, computational problems may arise for various reasons, such as no events for one of the clinical outcomes or severe multicollinearity. In

these cases, we will document the problem and fit a further simplified imputation model that pools one or more of these clinical outcomes together. Another potential modification to the imputation model is the use of individual items rather than total adjusted Constant-Murley score if for some patients there were missing items for a particular assessment.

Incorporating additional variables in the imputation model served two objectives. First, they can improve prediction of clinical outcomes used to construct the primary endpoint. Second, they can be used to address missing data on the secondary and tertiary endpoints. Among the variables included in the imputation model to support these objectives are the Oxford Shoulder score, EQ-5D-5L summary score and demographic variables (age, gender BMI and primary diagnoses). For the Oxford Shoulder score and EQ-5D-5L summary score separate variables for scores obtained at each assessment will be created and included in the imputation model.

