### **3.3 Study Population**

157 non-randomised subjects will be recruited from up to 20 sites. Investigational sites will be located in the European Union and Canada. A maximum of 30 subjects may be recruited from one site. More than one implanting surgeon may recruit subjects at each site as a designated sub-Investigator.

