- Appendix: Tables, Listings and Graph Shells

List of Abbreviations

AE	Adverse Event
BMI	Body Mass Index
CIP	Clinical Investigational Plan
n	Non-missing data
PG	Performance Goal
PMCF	Post Market Clinical Follow-Up
SAP	Statistical Analysis Plan
SD	Standard Deviation

1. Study Design

This study is designed as a prospective, multi-centre, non-comparative, uncontrolled Post Market Clinical Follow-Up (PMCF) Study.

There will be 157 patients with the GLOBAL ICON Stemless Shoulder System in Total Shoulder Arthroplasty in up to 20 sites located in the United Kingdom, the Netherlands, Germany and Canada. A maximum of 30 subjects may be recruited from one site. More than one implanting surgeon may recruit subjects at each site. A complete description of the methods for determining sample size is contained in Section 7.

Patients will be followed after surgery at several times: immediate Post-Op, 3-, 12-, 24-, 60- and 120-months. The data up to and including 24-month follow-up visit will be used to determine the effectiveness and safety of the device. The primary, safety, secondary and tertiary objectives are presented below.

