The sample size was determined based on the primary endpoint using the one-sample exact-test of a proportion as implemented in PROC POWER in SAS, version 9.3 or higher. For the calculation, we assume the composite success proportion at 24 months after surgery is 85% and implement a one-sided test at the 0.025 alpha-level to determine the minimal N which provides more than 80% power; this sample size is 133. To accommodate potential 15% attrition, the sample size will be increased to 157.

The sample size applies to patients enrolled and actually treated. Some patients who were enrolled in a study may not be ultimately treated for various reasons. Patient enrolment will continue until the proposed sample size for treated patients is complete.

NOTE: Although the sample size was originally determined based on the anticipated use of a one-sample exact-test of a proportion, it has been determined after enrolment was

complete that a one-sample Z-test of a proportion using a normal approximation would be utilized in the final primary endpoint analysis to facilitate data imputation methods.

9. Analyses to be Conducted

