9.4 Hypothesis Testing of Primary Endpoint

The primary endpoint analysis will seek to demonstrate that at the 24 month visit after surgery, the composite success (p), which is based on four study outcomes (radiograph demonstrating no continuous radiolucent line around the humeral component, adjusted Constant-Murley Score > 85, no removal of the humeral component, no serious adverse events related to the device), is significantly greater than a performance goal (PG) of 75%. The null and alternative hypotheses for this endpoint are as follows:

Null hypothesis H_{01} : $p \leq 75\%$

Alternative hypothesis H_{A1} : $p > 75\%$

The null hypothesis will be rejected and the alternative hypothesis will be accepted if the lower bound of a two-sided 95% confidence interval is greater than 75%. The performance goal of 75% used in the hypothesis test described above is based on the percentage of successful stemmed implants at the 24 month visit reported elsewhere using a similar definition of success [4]. Therefore, the hypothesis test implies a comparison to performance of stemmed implants. In a prior study, non-inferiority of the Simpliciti stemless humeral device to stemmed devices was demonstrated using a PG of 65% (75%-10% non-inferiority margin) [4]. Therefore, the current study sets a higher bar to establish successful performance of Global Icon when compared to the study evaluating the Simpliciti device.

Another objective using the same endpoint is to establish non-inferiority of Global Icon to Simpliciti conditional on rejection of H_{01} . To do so a PG or non-inferiority margin of 78.74% (Simpliciti success percentage of 88.74% [5] -10%) is selected. The null and alternative hypotheses for this objective are as follows:

Null hypothesis H_{02} : $p \leq 78.74\%$

Alternative hypothesis H_{A2} : $p > 78.74\%$

The null hypothesis will be rejected and the alternative hypothesis will be accepted if the lower bound of a two-sided 95% confidence interval is greater than 78.74%. Notably,

simultaneous testing of these nested null hypotheses (H_{01}, H_{02}) does not inflate the Type I error rate [6,7].

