9.5.2 Sensitivity Analyses Incorporating Site Variation

In this study, implants are implanted within study sites and therefore may not be independent. Therefore, as a sensitivity analysis, a beta-binomial model will be used for incorporating possible between-site variability on implantation success [9]. In this model the number of implant successes (X_i) within each site follows a binomial distribution, $X_i | p_i \sim \text{Binomial}(n_i, p_i)$, with the proportion of successes (p_i) across sites following a beta distribution, $p_i \sim \text{Beta}(\mu, \theta)$ with $\mu = \alpha/(\alpha + \beta)$ and $\theta = 1/(\alpha + \beta)$ (where α and β are positive-valued parameters of the beta distribution). This is a random-effects model with a

mean success rate across sites (μ) that allows for variation by site (θ). The model is estimated using NLMIXED via the BETABIN SAS macro. In the absence of variation in the success rate across sites (i.e., $\gamma < .000001$, where $\gamma = \theta/(1 + \theta)$), the normal approximation to the binomial will be used. As noted in 9.8.4, the analysis is repeated in each imputed data set and thereafter aggregated.

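### The SAP does not name site in its imputation model but fits the by-site sensitivity model to the imputed data, so that check modestly understates site variation if sites differ

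*SAP*

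**What the plan says.** SAP 9.5.2 accepts that outcomes within a site may be correlated and states that "a beta-binomial model will be used for incorporating possible between-site variability on implantation success". It has a mean success rate mu and a site-variation parameter, expressed as gamma, the intra-site correlation. If gamma is below .000001, the analysis reverts to the ordinary normal approximation with no site term. The model is not fitted to the raw data: "As noted in 9.8.4, the analysis is repeated in each imputed data set and thereafter aggregated".

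SAP 9.8.4 sets 50 imputations pooled by Rubin's method. SAP 9.8.5 uses one imputation model for the primary and the non-survival secondary and tertiary endpoints. It contains the four components of the composite (Constant-Murley by assessment). It then continues: "Among the variables included in the imputation model to support these objectives are the Oxford Shoulder score, EQ-5D-5L summary score and demographic variables", namely age, gender, BMI and diagnosis, with Oxford and EQ-5D-5L entered by assessment. Site is named neither there nor elsewhere in SAP 9.8.

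On scale, SAP section 1 says "There will be 157 patients with the GLOBAL ICON Stemless Shoulder System in Total Shoulder Arthroplasty in up to 20 sites", and Protocol 3.3 adds "A maximum of 30 subjects may be recruited from one site".

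**The concern.** The sensitivity model has a site term, and the listed imputation model that feeds it does not. A missing outcome at a weak or strong site is then drawn towards the all-site rate, which pulls the completed site rates together. A check meant to show whether sites differ therefore leans towards finding that they do not.

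This is the only planned analysis of site variation; the other sensitivity analysis (SAP 9.9) repeats the analyses in the Per Protocol Population. Clustering can matter here: the cap of 30 per site allows as few as six sites (157/30 = 5.2), and Table 1 of the Protocol has the site complete the Constant-Murley score, so differences between assessors are plausible.

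**Working it through.** **Inputs from the documents.** N = 157 in up to 20 sites, maximum 30 per site (SAP 1, Protocol 3.3); assumed success 85%, performance goal 75%, attrition 15%, or 0.15 x 157 = 23.6 subjects (SAP 8, 9.4); 50 imputations with Rubin pooling (SAP 9.8.4). **Assumed, because the documents give no value:** intra-site correlation (ICC) 0.02-0.10, the actual site sizes, and values missing completely at random.

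**The plan's own figure.** SAP 8 says: "implement a one-sided test at the 0.025 alpha-level to determine the minimal N which provides more than 80% power; this sample size is 133". With the exact binomial test at N = 133, success needs at least 110 responders; alpha is 0.0223 and power at 85% is 80.8%. (N = 132 already gives 81.8%; the difference of one is immaterial here.) 133/0.85 = 156.5, rounded up to 157. The inputs are therefore read as intended.

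**Dilution of gamma.** Let m be the share imputed without site and with no informative auxiliary variable. Two subjects in a site keep their correlation only if both are observed, so the ICC in the completed data is ICC x (1 - m)^2. At m = 0.15 the factor is 0.85^2 = 0.7225, a fall of about 28%: 0.05 becomes 0.036 and 0.10 becomes 0.072.

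**Standard error after Rubin pooling.** With k equal sites, pq = 0.85 x 0.15 = 0.1275, n_obs = 157(1 - m) and n_miss = 157m:

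- True variance = pq/n_obs x [1 + (n_obs/k - 1) x ICC]
- Pooled variance without site = pq/157 x [1 + (157/k - 1) x ICC x (1 - m)^2] + m^2 x pq x (1/n_miss + 1/n_obs)

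For k = 20, ICC = 0.10, m = 0.15, the true variance is 0.001497 (SE 0.0387). The pooled variance is 0.001214 + 0.000143 = 0.001357 (SE 0.0368). The ratio is 0.952. The second term is the between-imputation variance, which offsets part of the dilution.

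| Pooled SE / true SE | ICC 0 | ICC 0.02 | ICC 0.05 | ICC 0.10 |
|---|---|---|---|---|
| 15% missing, 20 sites | 1.000 | 0.987 | 0.971 | 0.952 |
| 15% missing, 10 sites | 1.000 | 0.973 | 0.947 | 0.923 |
| 15% missing, 6 sites | 1.000 | 0.959 | 0.927 | 0.903 |
| 5% missing, 20 sites | 1.000 | 0.995 | 0.989 | 0.982 |

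**Simulation of the planned steps.** 2,500 replicates per setting, one binary composite, 15% missing completely at random, 50 imputations, maximum-likelihood beta-binomial fit in each, Rubin pooling. Each cell shows site omitted / site included as a random effect, with no auxiliary score.

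| Setting | Mean gamma | 95% half-width (points) | Imputed sets reverting to no-site | P(lower bound > 75%) |
|---|---|---|---|---|
| 20 sites, ICC 0.05 | 0.038 / 0.060 | 6.6 / 6.9 | 33% / 24% | 0.778 / 0.752 |
| 20 sites, ICC 0.10 | 0.068 / 0.101 | 7.0 / 7.3 | 16% / 11% | 0.729 / 0.704 |
| 8 sites, ICC 0.05 | 0.032 / 0.050 | 7.1 / 7.7 | 31% / 22% | 0.721 / 0.683 |
| 8 sites, ICC 0.10 | 0.060 / 0.090 | 7.9 / 8.7 | 15% / 10% | 0.643 / 0.596 |

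With an earlier outcome available for every missing subject, at ICC 0.10, gamma is 0.085 / 0.094 and the half-width 7.0 / 7.0 (20 sites); with 8 sites they are 0.077 / 0.086 and 8.2 / 8.4.

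**Candidate remedies.** With 20 even sites and one earlier score, and a complete-data ICC of 0.041-0.043, imputation without site gave 0.034-0.037, imputation with fixed site dummies gave 0.056, and fitting to observed outcomes only gave 0.041-0.042. In a further run (continuous score cut to give 85% success, 500 replicates, 5 imputations) with complete-data ICC 0.050-0.052, fixed dummies gave 0.060-0.066, against 0.044-0.047 without site. Fixed dummies did better only with fewer, larger sites: for 10 unequal sites at ICC about 0.10 they gave about 0.105, against 0.085-0.092 without site.

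**The case against.** The strongest reply is that the effect is small in the trial as planned. The imputation model contains Constant-Murley, Oxford and EQ-5D-5L at every assessment, and these carry much of any site difference. The 15% is a ceiling in the Protocol synopsis. The 24-month window runs to day 1644, and withdrawals with a continuous radiolucent line, component removal or device-related serious event count as failures and are not imputed. All of this stands and limits the size. It does not remove the direction, and subjects who leave before an informative score would retain more of the loss.

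It is also fair that the list opens with "Among", so site is not excluded. But nothing commits the sponsor to including it either.

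Some under-coverage comes from the beta-binomial fit itself: at ICC 0.10 with no missing data, coverage of the nominal 95% interval was 91.6% with 20 sites and 87.0% with 8. Adding site to the imputation would not cure that.

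A reader might infer two stronger things. One is that the primary result is affected. It is not affected by this mechanism: the decision in SAP 9.4 and 9.5 rests on a Z-test with no site term, and 9.5.2 carries no decision rule. The other is that success is overstated because weaker sites lose more patients. The documents give no attrition by site, and the calculations assume missingness unrelated to site or outcome, so they do not support it.

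**Conclusion.** The point holds as a modest weakness in one sensitivity analysis. If sites differ and site is left out of the imputation, gamma is understated, reversion to the no-site interval is somewhat more likely and the interval is slightly too narrow. At 15% missing with no informative earlier score, gamma falls by about 28%, and the pooled SE is about 1-5% too small with 20 sites and up to about 10% with 6. With useful earlier scores, or about 5% missing, the shortfall is much smaller (0.5-2% in SE at 5% missing with 20 sites). At zero intra-site correlation it vanishes. These sizes rest on assumed correlations of 0.02-0.10, even sites in the closed form, and values missing completely at random.

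**What to change.** In SAP 9.5.2, add that the beta-binomial model will also be fitted to subjects whose 24-month composite status is known, including withdrawals already classed as failures. Report gamma and the interval from that fit beside the imputed-data result.

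In SAP 9.8.5, state whether site enters the imputation for this analysis. If it does, use a random or shrunken site effect in the Constant-Murley step. Fixed site dummies overstate site variation when sites are small, and they add to the computational risk that 9.8.5 already anticipates.

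The cost is SAP wording and a few lines of code, with no new data: the site number is already part of every subject identifier. The downside is one extra analysis with slightly fewer subjects, which relies on missingness being unrelated to outcome within site. Because known early failures are kept while other withdrawals drop out, its mean success rate may sit slightly low; its main use is the comparison of gamma.

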Appendix: Tables, Listings and Graph Shells

The document that contains the tables, listings and graphs shells is entitled Study DPO_CT1401_ICON Table Figure and Listing Shells.

End of Document
